# **Physical therapy treatment once a month versus once a week for posture improvement in children and adolescents**

**Document Date: October 31, 2016**

**Clinical Trials NCT03046472**

**Background:** Life time prevalence of Low Back Pain among Children and Adolescent ranges from 32% to 66%. This prevalence gets higher with age and among 17 years old it's equal to prevalence among adults. Previous episode of Low Back pain is a predicting risk factor to the next one, hence we should do preventative care at a young age, even before the first attack occur. Poor posture was found as one of the risk factors for Low Back Pain in children. Adolescence with neutral posture had less prevalence of Low Back Pain than those with poor posture. Prolong slouch sitting was associated with Low Back Pain. Prevention education programs, focusing on knowledge, did not show effective change in posture behavior. Hence, the researchers concluded that it's better if they focus on exercise

**Research objective:** comparison between physical therapy treatment for good posture once a week versus once a month, on postural behavior, thorax curve angle and Low Back Pain

**Research design:** randomize, Interventional, blinded

(Late note: this trial ended to be non-randomized due to unwillingness of participants in once a week program, therefore once in a week program was offered to everyone and only 17 out of 50 chose it).

**Population:** the study will include 50 children and adolescents age 10-18 years suffering from poor back posture, with or without Low Back Pain

**Procedure:** The study will consist of two groups: both groups will get personal meeting once a month and a program of exercising at home every day. Treatment group will have in addition group meeting once a week and control group not. The intervention program will include physical awareness and practice for good posture, and exercises for flexibility, strength and muscle endurance.

Study Phase	Executed by
First meeting	
Providing explanation and get signatures from participants and their parents on consent forms	[name] PBT MPE student
Participant and parents answering questionnaires Inclinometer test Postural observation	[name] BPT blinded to group allocation
Comprehensive physical therapy Checkup Treatment including tailored exercise plan and instructions for postural awareness	[name] PBT MPE student
Allocation for study groups	[name] PBT MPE student
Second meeting after 4 weeks	
Treatment including adjusting tailored exercise plan and instructions for postural awareness	[name] PBT MPE student
Third meeting after 8 weeks	
Treatment including tailored adjusting exercise plan and instructions for postural awareness	[name] PBT MPE student
Fourth meeting after 12 weeks	
Participant and parents answering questionnaires Inclinometer test Postural observation	[name] BPT blinded to group allocation
Last treatment of trial including tailored adjusting exercise plan and instructions for postural awareness. ( if goals have not been achieved yet, Treatment will go on in the clinic after trial is finished)	[name] PBT MPE student

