**Measurement tools:**

Digital Inclinometer for measuring thorax curve angle.

Postural observation for measuring postural habits.

Back pain and postural habits questionnaire for measuring LBP on VAS SCALE, postural knowledge and habits of participant, including demographic data.

**Research hypothesis:** postural behavior, thorax curve angle and Low Back Pain will get better in both groups but more in the treatment group.

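### Does a pain hypothesis worded only as improvement conflict with an entry rule that admits children without pain?

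*Protocol*

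**What the plan says.** - **Population:** "the study will include 50 children and adolescents age 10-18 years", described as "suffering from poor back posture, with or without Low Back Pain". Poor posture is required for entry; pain is not.
- **Background:** the case for early treatment is that an earlier episode of back pain predicts the next, "hence we should do preventative care at a young age, even before the first attack occur". Poor posture is presented as a risk factor for pain.
- **Research objective:** weekly and monthly treatment are compared on postural behavior, thorax curve angle and low back pain. Neither prevention nor new pain is named.
- **Measurement tools:** "Back pain and postural habits questionnaire for measuring LBP on VAS SCALE". The recall period is not given.
- **Procedure table:** the same assessments ("Participant and parents answering questionnaires Inclinometer test Postural observation") appear at the first meeting and at the fourth, after 12 weeks.
- **Research hypothesis:** "postural behavior, thorax curve angle and Low Back Pain will get better in both groups", and more so in the treatment group.
- **Research design, late note:** "this trial ended to be non-randomized due to unwillingness of participants in once a week program". Of the 50 children, 17 chose the weekly program, which leaves 33 on the monthly one.

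The protocol gives no rule for comparing the VAS scores between groups.

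**The concern.** A pain-free child sits at the floor of the VAS and can only stay at 0 or get worse. For such children, whom the protocol deliberately admits, improvement in pain cannot occur. The event that the preventive argument points to, new pain by week 12, is not named.

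Two consequences would matter:

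1. A single VAS comparison over all children dilutes any relief in those with pain, and it cannot separate relief from prevention.
2. Only children with pain can improve. If the self-selected groups differ in the share with pain at entry, natural recovery could pass for a treatment effect in an unadjusted analysis of change.

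The two posture outcomes are untouched.

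**Working it through.** The protocol states no power, effect size or standard deviation, so there is no figure of its own to reproduce. The check is first a reading of the text, then an illustration of size.

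**Reading.** The hypothesis predicts what happens in the groups. If a share q of a group has pain and those children improve by m points on average while the rest stay at 0, the group mean improves by q × m. That is above zero whenever q and m are. The entry rule and the hypothesis can therefore both hold.

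**Inputs.** From the protocol: 50 children, 17 weekly and 33 monthly. Assumed: q between 0.32 and 0.66 (the Background's lifetime prevalence, used only as a range for pain at entry); in children with pain, a mean fall of 1 point (monthly) and 3 points (weekly), so an effect of 2, with SD of change 2; no change in pain-free children; two-sided alpha 0.05.

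**Children at the floor.** 50 × (1 − 0.66) = 17 and 50 × (1 − 0.32) = 34.

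**Dilution.** The whole-sample difference is q × 2. The variance of change in a group with mean fall μ among those with pain is q(2² + μ²) − (qμ)².

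- q = 0.32: difference 0.64. Variances 3.24 (weekly, μ = 3) and 1.50 (monthly, μ = 1), pooled SD √[(17 × 3.24 + 33 × 1.50)/50] = 1.45, power about 32%.
- q = 0.66: difference 1.32. Variances 4.66 and 2.86, pooled SD 1.86, power about 66%.
- q = 1: difference 2.00, SD 2, power about 92%.

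**Would restricting to children with pain, or adjusting, be clearly better?** Simulated power, 4,000 trials per case:

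| Analysis | q = 0.32 | q = 0.66 |
|---|---|---|
| All 50, unadjusted | 31% | 65% |
| All 50, adjusted for pain status, ordinary errors | 39% | 75% |
| All 50, adjusted, HC3 errors | 31% | 70% |
| Children with pain only | 41% | 75% |

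The HC3 row is the fair comparator for the adjusted analysis, because pain-free children vary less and ordinary errors reject too often when pain shares differ widely (8% under the null below). On that footing the pain-only analysis is ahead, 41% against 31% and 75% against 70%. The order can reverse: if 20% of pain-free monthly children, and no weekly ones, developed 3 points of new pain, the adjusted analysis with ordinary errors would reach 71% and 83%, against 41% and 75% for pain-only.

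**Imbalance with no true effect.** The unadjusted bias is the difference in pain shares times the natural improvement (1 or 2 points).

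- 66% v 32%: 0.34 × 1 = 0.34 and 0.34 × 2 = 0.68 points. False-positive rate 16% and 30% unadjusted; 8% adjusted with ordinary errors; 3% to 4% with HC3.
- 55% v 45%: 0.10 × 1 = 0.10 and 0.10 × 2 = 0.20 points. False-positive rate about 7% to 9% unadjusted.

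**Yield of naming new pain.** At q = 0.32 there are about 12 weekly and 22 monthly pain-free children (17 × 0.68 = 11.6; 33 × 0.68 = 22.4). Even 0 of 12 against 4 of 22 gives Fisher p = 0.27. With monthly rates of 10% to 30%, halved in the weekly group, power is about 4% to 14% over the range of q. Among children with pain, 5 v 11 or 11 v 22 give 95% interval half-widths of t × 2 × √(1/n₁ + 1/n₂) = 2.3 and 1.5 points.

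**The case for a change.** The strongest case for a change is that the enrolled population and the pain hypothesis are both protocol content. A later analysis plan could choose a model, but it would inherit a hypothesis that cannot apply to some of the children. Because families chose their group, a difference in baseline pain is plausible. Splitting the hypothesis into relief and new pain, tabulating baseline pain and adjusting for it would need no new data.

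Part of this stands. The wording is incomplete for pain-free children, and a whole-sample VAS result would mix relief with prevention. The rest does not carry a change:

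- The hypothesis is about groups, and the preventive argument belongs to the Background. Treating posture early can itself be the preventive step, so a 12-week posture trial need not make new pain an endpoint.
- The imbalance arises from self-selection, not from the entry rule. The 16% to 30% figure also needs opposite ends of a lifetime-prevalence range in the two groups.
- Baseline adjustment, robust errors and baseline tables are usual content of a statistical analysis plan.
- The two-part hypothesis could support description only, from scores the questionnaire already collects.

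**Conclusion.** No change follows. The floor effect is a limit on interpretation, not a contradiction: a group mean can improve although some members cannot. Under the assumptions above, the whole-sample effect shrinks from 2 points to between 0.64 and 1.32. The true size is unknown, because the protocol does not give the share with pain at entry, and without a recall period a child with no current pain might still score above 0.

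The more serious harm, a spurious pain effect, depends on an unadjusted analysis that the protocol does not prescribe and shrinks quickly with milder imbalance. An analyst comparing baseline and week-12 VAS in self-selected groups would sensibly adjust for the baseline score and show it by group. Whether to analyse all children or only those with pain is a fair trade-off: the first keeps any preventive effect, and the second has somewhat more power for relief alone. Rewording the hypothesis would correct no stated rule, number or conclusion.

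### Masking the tester to group protects the weekly-versus-monthly comparison, but not the claim that observer-rated posture improves within both groups

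*Protocol*

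**What the plan says.** The Research hypothesis has two parts for postural behavior, thorax curve angle and low back pain, namely that they "will get better in both groups but more in the treatment group". One part concerns change from week 0 to week 12 within each group. The other is a contrast between groups, and it matches the Research objective, which compares the weekly with the monthly programme.

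The procedure table has two assessment visits, the first meeting and the "Fourth meeting after 12 weeks". Each lists the same tasks, "Participant and parents answering questionnaires Inclinometer test Postural observation", and gives the tester the same description, "BPT blinded to group allocation". No other masking of the tester is described, and there is no mention of recordings or of scoring in shuffled order.

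Under Measurement tools, the protocol lists "Postural observation for measuring postural habits", without a scale or scoring procedure. It also lists a questionnaire that covers back pain and "postural knowledge and habits of participant, including demographic data", and, for a separate outcome, "Digital Inclinometer for measuring thorax curve angle".

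The Procedure paragraph says that "both groups will get personal meeting once a month and a program of exercising at home every day". There is no untreated arm.

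**The concern.** Masking to allocation hides which programme a child followed. It does not hide that the child has followed one. At the first meeting the tester sees untreated children, and the table lists allocation after testing, so there is no allocation to hide at that point. At week 12 the tester sees only treated children. Visit and treated status coincide for everyone.

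The postural observation is a human judgement. If the tester expects children to look better after 12 weeks, the week-12 ratings can drift in the favourable direction although no child has changed. Within a group, that drift cannot be told apart from improvement, and no later analysis can separate the two.

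This is a question of measurement: is the recorded change real? It differs from the question whether a real change was caused by the programme, which the lack of an untreated arm leaves open. What is at stake is a conclusion that posture improved under both programmes when part or all of the change lies in the rating.

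**Working it through.** **Step 1. What group masking covers.** Let the observed mean change in a group be the true change plus a rater drift *b* between visits. The tester does not know the group, so take *b* as the same in both.

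- Between groups: (true weekly change + *b*) − (true monthly change + *b*) = true weekly change − true monthly change. The drift cancels.
- Within a group: true change + *b*. The drift remains in full.

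So the second half of the hypothesis is protected and the first half is not.

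**Step 2. Whether another measure of postural habits fills the gap.** The questionnaire is answered by children and parents who know that treatment was given, so it is open to the same kind of expectation. The inclinometer measures thorax curve angle, which the hypothesis lists as a separate outcome. Neither supplies a visit-masked measure of postural behavior.

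**Step 3. Size, as an illustration.** The protocol gives no SD, reliability, significance level or within-group test, so there is no figure of its own to reproduce.

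Inputs from the protocol: 50 children, of whom 17 chose the weekly programme (late note under Research design). That leaves 50 − 17 = 33 in the monthly group if all were followed.

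Assumptions: true change zero; drift of 0.2 or 0.3 SD of the rating; correlation 0.6 between visits; a paired t-test in each group, two-sided at 5%; groups independent given the drift.

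Formulas: SE of the mean change in SD units = √(2(1 − r)/n); noncentrality = drift/SE. The probability of a significant improvement is the upper-tail area of the noncentral t beyond the critical value.

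- n = 17: SE = √(0.8/17) = 0.217; critical t (16 df) = 2.120
- n = 33: SE = √(0.8/33) = 0.156; critical t (32 df) = 2.037

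| Drift | Weekly (17) | Monthly (33) | Both groups |
|---|---|---|---|
| 0 | 0.025 | 0.025 | 0.025 × 0.025 = 0.0006 |
| 0.2 SD | 0.137 | 0.238 | 0.137 × 0.238 = 0.033 |
| 0.3 SD | 0.255 | 0.464 | 0.255 × 0.464 = 0.118 |

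The hypothesis asserts improvement in both groups, so the last column is the relevant one: about 3% to 12%, against about 0.06% without drift.

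**Step 4. Sensitivity to the correlation.** At 0.3 SD drift, r = 0.5 gives 0.213 × 0.387 = 0.082, and r = 0.7 gives 0.323 × 0.578 = 0.187.

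**The case against.** The strongest reply is that the protocol claims no more than it delivers. It says that the tester is masked to group and never says to visit. Masking to group is the masking that the stated objective needs, and an equal drift leaves that comparison untouched. This stands. A reader might infer that calling the design blinded contradicts the procedure table, or that the weekly-versus-monthly result is biased or compressed because ratings crowd at the good end of a scale. The document supports neither. It makes no claim of visit masking, and it gives no scale from which a ceiling could be inferred.

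A reader might also infer that the tester's rating is the only evidence on postural habits. It is not, because the questionnaire asks about them too. That evidence is self-report after treatment, so it does not remove the problem, but it should be acknowledged.

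The drift and the correlation are assumed, and the calculation shows only what an assumed bias would do. It is tempting to quote the single-group figure of about 46% for the 33 monthly children at 0.3 SD, but the hypothesis requires improvement in both groups, and the joint figure is much lower.

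Finally, with no untreated arm and children selected for poor posture, the within-group change could not be read as a treatment effect even with perfect visit masking. This is correct, and it limits what a remedy can buy. It does not dispose of the point: whether a change occurred at all comes before the question of its cause, and the protocol puts the within-group claim in its hypothesis.

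**Conclusion.** The point holds for one outcome and one half of the hypothesis: the within-group improvement in the live-rated postural observation. Group masking cannot protect it, because every week-12 child has been treated and the tester sees the child at that meeting. The protocol does not state that the tester is aware of the visit; this follows from the observation being listed as a step of the week-12 meeting, with no recording or shuffled scoring described. The between-group comparison is not affected as long as the drift is equal in the two groups.

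The size of any bias is unknown. Under the assumptions in the working, a false claim of improvement in both groups rises from about 0.06% to between 3% and 12%. These figures show how the claim responds to a modest drift; they do not estimate what happened in this trial. The point deserves a change because the remedy costs almost nothing and alters what may be concluded.

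**What to change.** 1. At week 12, withhold the child's week-0 observation score and angle from the tester. This does not hide the visit, but it stops the earlier value from guiding the later one. It costs a sealed baseline sheet.

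2. State that the within-group change in the live postural observation is descriptive and does not by itself support the claim of improvement in both groups. Keep the observation for the weekly-versus-monthly comparison. The cost is a weaker within-group statement for this outcome. This wording can still be adopted if, as the late note suggests, the trial has already run.

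3. As an optional stronger measure, record the observation at both visits under a code without date, and have the same tester score all recordings in one random order without knowing the visit. For 50 children this means 2 × 50 = 100 recordings. It is possible only where recordings can still be made at both visits and families agree to the filming of minors. It cannot be done for children whose week-0 assessment is past. Being filmed may also alter the habitual posture under study, and scoring refusers live would mix two methods.

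Replacing the observation by the inclinometer angle is not a remedy. The angle is a separate listed outcome, so this would drop the claim about postural behavior instead of protecting it.

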**Measurement tools:**

Digital Inclinometer for measuring thorax curve angle.

Postural observation for measuring postural habits.

Back pain and postural habits questionnaire for measuring LBP on VAS SCALE, postural knowledge and habits of participant, including demographic data.

**Research hypothesis:** postural behavior, thorax curve angle and Low Back Pain will get better in both groups but more in the treatment group.
